9.4.3 ANALYSIS OF SECONDARY ENDPOINTS

Secondary endpoints for changes in stigma, depression, anxiety, suicidal ideation, social isolation, and QOL will be analyzed with similar approaches. Covariates prognostic for each of these secondary endpoints will be pre-specified prior to formulation of the final SAP.

We will perform a causal mediation analysis¹⁰⁵ to evaluate the degree to which the effect of treatment (BRIGHT) on the primary outcome (change in IMAGE-HN scores between baseline and 6-month follow-

up) is mediated by changes in candidate mechanism of change variables (between baseline and 3-month follow-up, covariates). We will use structural equation modeling to perform mediation analysis for each of the following mechanism of change variables: (1) BICSI Positive Rational Acceptance score;⁵⁵ (2) BICSI Avoidance score;⁵⁵ (3) BICSI Appearance Fixing score;⁵⁵ and (4) Automatic Thoughts Questionnaire score.⁹⁶ This approach allows for ease of interpretation and estimation in Mplus. Model fit will be assessed using chi-square, comparative fit index (>0.95), root mean square of approximation (<0.06), and standardized root mean square residual (<0.08).^{106,107} Missing data will be handled with maximum likelihood estimation.¹⁰⁸ If we encounter challenges in model stability, we will use Baron and Kenny's approach.¹⁰⁹ The following regression analyses will be performed: (i) the outcome (IMAGE-HN score) is regressed on a treatment group indicator (BRIGHT, AC) to obtain a regression model measure of the intervention effect; (ii) the candidate mediator (e.g., BICSI Avoidance score) is regressed on the treatment group indicator (BRIGHT, AC) to obtain a measure of the intervention's effect on the covariate; and (iii) the outcome (IMAGE-HN score) is regressed on both the treatment group indicator (BRIGHT, AC) and the candidate mediator (e.g., BICSI Avoidance score). We will conclude that the candidate mediator in fact mediates the effects of the intervention if: (1) in both analyses (i) and (ii), the treatment group indicator is significant; and (2) in analysis (iii), the candidate mediator is significant and the coefficient estimate of the treatment group indicator is smaller in absolute value than its counterpart in analysis (i). If we detect mediation, we will consider Sobel's test to assess the significance of the mediation effect. We will examine standardized coefficients for the direct pathways and the mediation pathways to compare the strength of each. If the cluster effect is significant, we will conduct multilevel mediation analysis for partially nested data.¹¹⁰ The study design consideration and analytic plan follow recommended criteria to provide evidence for mechanism of change above and beyond statistical mediation.¹¹¹ We will also explore mediation analysis using multiple mediators.^{112,113} Finally, to better understand the temporal dynamics of causal intervention effects, we will adapt Goldsmith's approach to: (1) examine the intervention effect on outcomes at different time points; (2) examine the intervention effect on hypothesized mediators at different time points; (3) examine the relation of the mediator to the outcome at different time points; and (4) determine if there is temporal variation in the mediating process.¹¹⁴ If there is temporal variation in the mediating process, we will fit a multilevel mediation model using the approach described by Preacher.¹¹⁵

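### As described, the single-mediator SEMs in Section 9.4.3 are just-identified, so their fit cut-offs are met for any data and cannot flag a wrong model

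*Protocol*

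**What the plan says.** All of this is in Protocol Section 9.4.3.

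- **Method.** "We will use structural equation modeling to perform mediation analysis for each of the following mechanism of change variables". The four variables are the three BICSI subscale scores (Positive Rational Acceptance, Avoidance, Appearance Fixing) and the Automatic Thoughts Questionnaire score.
- **Effect studied.** The aim is the degree to which the "effect of treatment (BRIGHT) on the primary outcome (change in IMAGE-HN scores between baseline" and 6 months) "is mediated by changes in candidate mechanism of change variables (between baseline and 3-month follow-up, covariates"). The section labels this a causal mediation analysis.
- **Paths.** Direct and mediated paths are both estimated: "We will examine standardized coefficients for the direct pathways and the mediation pathways to compare the strength of each". No path is said to be fixed at zero, and no latent variable or item-level measurement model is described.
- **Fit criteria.** "Model fit will be assessed using chi-square, comparative fit index (>0.95), root mean square of approximation (<0.06") and "standardized root mean square residual (<0.08").
- **Fallback if the models are unstable.** In regression (ii) the mediator "is regressed on the treatment group indicator (BRIGHT, AC) to obtain a measure of the intervention's effect on the covariate". In regression (iii) the outcome "is regressed on both the treatment group indicator (BRIGHT, AC) and the candidate mediator". In (ii) the word covariate means the mediator itself, so the same word in the parenthesis above probably labels the mediators too.
- **Further models.** Multiple-mediator, longitudinal and multilevel variants are named later in the section, as exploratory or conditional steps.

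**The concern.** A fit index compares the covariances that a model implies with those observed. It can fail only if the model imposes a restriction. A model with one treatment, one observed mediator and one observed outcome, with all three paths free, imposes none. The protocol nevertheless attaches numerical cut-offs to these models, and they are the only model check that the section states for them.

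The mechanism aim is a listed secondary objective. A report showing CFI 1 and RMSEA 0 for all four mediators could be taken as support for the mechanism, although those values would appear under any truth. The assumption that decides whether the indirect effect is causal is that mediator and outcome share no unmeasured cause. Randomisation does not secure it, because only arm is randomised, and the fit indices do not address it.

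**Working it through.** The protocol gives no degrees of freedom and no figure to reproduce here, so the check counts moments and parameters.

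**1. Basic model.** Let X be arm, M the mediator change to 3 months and Y the IMAGE-HN change to 6 months.

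- Observed variances and covariances: 3 × 4 / 2 = 6.
- Parameters: var(X), path a (X→M), residual var(M), path b (M→Y), path c′ (X→Y), residual var(Y) = 6.
- df = 6 − 6 = 0. Chi-square is 0, CFI 1, RMSEA 0 and SRMR 0 for any data.

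**2. With covariates.** Conditional on k exogenous variables (arm included), the moments are 3 + 2k. The parameters are the slopes in the two equations plus 2 residual variances.

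| Specification | Moments | Parameters | df |
|---|---|---|---|
| Arm only | 3 + 2 = 5 | 1 + 2 + 2 = 5 | 0 |
| 8 covariates in both equations | 3 + 18 = 21 | 9 + 10 + 2 = 21 | 0 |
| Baseline M only in M equation, baseline Y only in Y equation | 3 + 6 = 9 | 2 + 3 + 2 = 7 | 2 |
| 8 covariates only in Y equation | 21 | 1 + 10 + 2 = 13 | 8 |

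Eight is the number of covariates that Section 9.4.2 names for the primary model, each counted as one column. Using them here is an assumption.

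**3. Four parallel mediators.** There are 5 endogenous variables, so moments = 15 + 5 = 20. Parameters with residual covariances fixed at zero: 4 + 4 + 1 + 5 = 14, so df = 6. Freeing the 6 residual covariances among mediators gives df = 0 again.

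**4. Simulation of the fit test.** n = 180, 2,000 runs per truth, assumed coefficients.

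| Truth | Largest chi-square, df = 0 model | Rejection rate, df = 2 variant |
|---|---|---|
| Real mediation | about 6e-13 | 5.7% |
| Reverse causation (Y→M) | about 4e-13 | about 85% |
| No M→Y effect, shared unmeasured cause | about 4e-13 | 5.4% |

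The df = 0 model never signals anything. The over-identified variant detects reverse causation in this setting, but rejects the confounded truth only at the nominal rate.

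**5. How much confounding matters (a separate question, all inputs assumed).** Take N = 180, 90 per arm, no clustering, a true b of zero, M shifted by a = 0.4 or 0.5 residual SD, and residual M–Y correlation ρ.

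- z for a: a / (2/√180). This is 2.68 for 0.4 and 3.35 for 0.5. Probability of significance 0.765 and 0.918.
- z for the estimated b: ρ√177 / √(1 − ρ²). This is 1.34, 2.72 and 4.18 for ρ = 0.1, 0.2 and 0.3. Probability of significance 0.267, 0.775 and 0.987.
- Both significant is approximately the product:

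| ρ | a = 0.4 | a = 0.5 |
|---|---|---|
| 0.1 | 0.765 × 0.267 = 20% | 0.918 × 0.267 = 25% |
| 0.2 | 0.765 × 0.775 = 59% | 0.918 × 0.775 = 71% |
| 0.3 | 0.765 × 0.987 = 76% | 0.918 × 0.987 = 91% |

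Simulations with a Monte Carlo interval for a·b (2,000 trials per setting) gave 19–25%, 54–70% and 76–91%. At ρ = 0 they gave 4–5%.

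**The case against.** **The equations are not written out.** The SAP, not shown, may give the two equations different covariates. Then df exceeds 0 and the indices test those exclusions. This stands. A reader might infer that the fit check guards against nothing in any version of the analysis. The documents do not support that, since the df = 2 variant above did detect reverse causation. The point holds for the model as described and for identical covariates in both equations.

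**The fit sentence may serve the later models.** Multiple-mediator and longitudinal models can be over-identified, and the cut-offs are reasonable there. This also stands. The defect is that the sentence is not limited to models where it can be informative.

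**No decision rests on fit.** The section attaches no consequence to passing. Its explicit criteria for concluding mediation, given for the regression fallback, rest on significance and on a smaller treatment coefficient. This is correct and lowers the severity.

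**The confounding percentages measure something else.** A reader might infer that saturation causes the 54–91% false findings at correlations of 0.2 and 0.3. It does not. They would be essentially the same if the fit sentence were deleted, and an over-identified model would miss the confounding too. The mediator shift and residual correlation have no anchor in the protocol, and therapist clustering is ignored.

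**A sensitivity analysis is SAP content.** Its absence from a protocol is not a finding, and none is claimed. It is offered as a useful replacement for a stated check that cannot fail. Measuring the mediator at 3 months and the outcome at 6 months helps with temporal order, but not with a shared cause.

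**Conclusion.** For the four single-mediator models as Section 9.4.3 describes them, df = 0 and the chi-square, CFI, RMSEA and SRMR criteria are satisfied by any data. That conclusion is algebraic. It rests on three readings of the text: observed scores, all paths free, and no covariate that appears in only one equation. The criteria gain content under equation-specific covariates or in over-identified models. They still do not address unmeasured mediator-outcome confounding.

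How far confounding could mislead depends on inputs that the protocol does not give. Under those assumed in step 5, even a residual correlation of 0.1 raises the rate of a spurious indirect effect from about 4–5% to about 19–25%. This is an illustration and not an estimate for this trial.

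The matter concerns a secondary mechanism analysis only. It is a low-severity point, worth considering because the remedy is cheap.

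**What to change.** 1. Restrict the fit cut-offs to models with positive degrees of freedom, and state the df wherever fit is reported. For the single-mediator models, say that they are just-identified and that fit is not assessed.
2. For each single-mediator model, report the indirect effect as a function of an assumed residual correlation ρ, and the ρ at which it reaches zero. Show that value beside any statement that mediation is supported.

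The second item needs only the fitted quantities. Let r be the correlation of M and Y given arm, and s_Y and s_M their residual SDs given arm (and given any shared covariates). Then b(ρ) = (s_Y / s_M) × [r − ρ√((1 − r²)/(1 − ρ²))], and the indirect effect is a × b(ρ). Setting ρ = 0 returns the usual estimate. The effect reaches zero at ρ = r.

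The cost is one changed sentence in the protocol or SAP and a small computation from the same fits, with no new data. The mechanism conclusion may become more cautious. The primary analysis and sample size do not change.

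### The fallback mediation regressions carry no baseline covariates and feed a fixed decision rule, so if they are used they can declare mediation where none exists

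*Protocol*

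**What the plan says.** Protocol section 9.4.3 announces the mechanism analysis with "We will perform a causal mediation analysis". The outcome is change in IMAGE-HN from baseline to 6 months. The mediators are changes from baseline to 3 months in three BICSI subscales and the Automatic Thoughts Questionnaire. Structural equation modelling is the main method. The alternative is conditional: "If we encounter challenges in model stability, we will use Baron and Kenny's approach".

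The fallback is written out in full:

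- Regression (i): "the outcome (IMAGE-HN score) is regressed on a treatment group indicator (BRIGHT, AC) to obtain a regression model measure of the intervention effect".
- Regression (ii): the mediator "is regressed on the treatment group indicator (BRIGHT, AC) to obtain a measure of the intervention's effect on the covariate". The covariate meant here is the mediator itself.
- Regression (iii): "the outcome (IMAGE-HN score) is regressed on both the treatment group indicator (BRIGHT, AC) and the candidate mediator".

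The protocol commits to concluding mediation if two conditions hold. The first is that "in both analyses (i) and (ii), the treatment group indicator is significant". The second is that in (iii) "the candidate mediator is significant and the coefficient estimate of the treatment group indicator is smaller in absolute value than its counterpart" in (i). Only after mediation has been declared will the team consider Sobel's "test to assess the significance of the mediation effect".

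By contrast, the primary model in section 9.4.2 adjusts for site, free flap reconstruction, baseline IMAGE-HN and five further baseline covariates.

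**The concern.** Randomisation protects regressions (i) and (ii). It does not protect the mediator coefficient in (iii), because nobody randomised patients to coping scores. If patients with worse baseline coping also have worse baseline IMAGE-HN, both change scores partly reflect their own starting values. They will then correlate within arm even when the mediator does nothing to the outcome. Regression (iii) reads that correlation as a mediator effect. BRIGHT need only shift the mediator and the outcome for the rule to be met.

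The rule has a second weakness. It requires a significant total effect, which mediation does not need. When the total effect is small, or the direct and indirect paths oppose each other, real mediation is missed. Sobel's test cannot recover it, because it is considered only after a positive declaration.

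At stake is the conclusion on the mechanism of change, which section 2.3.3 expects to help identify which therapeutic elements to optimise.

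**Working it through.** **Inputs from the protocol (section 9.2).** Target difference 9 points, SD 16, ICC 0.05, 9 clusters per arm with about 10 participants each, 90 participants per arm, two-sided alpha 0.05.

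**The plan's own figure.** Design effect = 1 + (10 − 1) × 0.05 = 1.45. SE = 16 × √(2 × 1.45/90) = 2.872. Noncentrality = 9/2.872 = 3.134. With 2 × (9 − 1) = 16 degrees of freedom, power is 83.67%, which matches the stated 83.7%. The protocol gives no error rate or power for the mediation rule.

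**Assumed inputs.** The protocol states no correlations or path sizes. Assumed here:

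- correlation ρ between baseline mediator and baseline IMAGE-HN of 0.3 to 0.7;
- baseline-to-follow-up correlation r of 0.5 or 0.7;
- BRIGHT shifts the mediator by 0.5 SD and the outcome by 9/16 = 0.56 SD;
- the mediator has no effect on the outcome;
- no clustering.

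**Why change scores do not remove the problem.** Write each follow-up score as r × baseline + treatment effect + independent noise, with unit variances. Within arm, each change score has variance (1 − r)² + (1 − r²) = 2(1 − r). The covariance between the two changes is (1 − r)²ρ. Their correlation is therefore ρ(1 − r)/2, although no mediation exists:

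- ρ = 0.3, r = 0.7: 0.3 × 0.3/2 = 0.045.
- ρ = 0.7, r = 0.5: 0.7 × 0.5/2 = 0.175. With N = 180 the Fisher z is √177 × atanh(0.175) = 2.35, so the mediator is significant in about 65% of trials.

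**Simulation of the exact rule, no mediation present** (N = 180, 4,000 trials per row, ordinary least squares on change scores; the adjusted column puts baseline outcome and baseline mediator in all three regressions):

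| ρ | r | Rule as written | Sobel also required | Rule, baseline-adjusted |
|---|---|---|---|---|
| 0.3 | 0.5 | 15% | 7% | 3% |
| 0.3 | 0.7 | 9% | 5% | 3% |
| 0.5 | 0.5 | 33% | 19% | 2% |
| 0.5 | 0.7 | 16% | 11% | 2% |
| 0.7 | 0.5 | 59% | 40% | 3% |
| 0.7 | 0.7 | 29% | 21% | 2% |

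A separate run under the same assumptions gave 9% to 55% as written and about 1% to 4% adjusted.

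**Mediation present.** Let a be the treatment-to-mediator path, b the mediator-to-outcome path, and c′ the direct effect, all in SD units. The comparator is joint significance of a and b.

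| a, b, c′ | Total effect ab + c′ | Rule as written | Joint significance |
|---|---|---|---|
| 0.5, 0.3, 0.4 | 0.55 | 84% | 89% |
| 0.5, 0.5, 0 | 0.25 | 31% | 92% |
| 0.5, 0.3, 0 | 0.15 | 15% | 89% |
| 0.39, 0.39, 0 | 0.15 | 13% | 74% |
| 0.5, 0.5, −0.25 | 0 | 2% | 91% |

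The loss comes from the total-effect step. With a total effect of 0.15 and SE of about √(4/180) = 0.149, the expected z is about 1.0, so step (i) is rarely passed. Across the runs near the planned 9/16 SD, detection was roughly 84% to 93% for the rule against 89% to 95% for the comparator.

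**What adjustment cannot do.** With an assumed residual mediator-outcome correlation of 0.3 from an unmeasured cause, false declarations were about 95% without baseline adjustment and 97% with it.

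**The case against.** The strongest case on the other side has five parts.

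- **It is only a contingency.** Each planned model has one observed mediator and one observed outcome, and such path models seldom fail. A reader might infer that this rule will decide the mechanism objective. The protocol does not support that, because structural equation modelling comes first. This stands and limits the importance of the point.
- **Change scores may remove the confounding.** If a stable trait acts equally at both times, differencing largely removes it: false declarations were then 1% to 3%. This also stands. Under ordinary regression towards each score's own mean, as in the first table, it does not.
- **The false-positive figures depend on correlations the protocol does not give.** They show what the rule permits and should not be read as this trial's known error rate.
- **At the planned effect, little power is lost.** A reader might infer that the rule will usually miss real mediation. At 9/16 SD it does not. The large losses need a smaller total effect or opposing paths. Asking first for a total effect also has some logic when the question is how much of that effect is mediated.
- **Other text may supply the covariates.** Section 9.4.3 promises prognostic covariates, but for stigma, depression, anxiety, suicidal ideation, social isolation and QOL. The stray word in the mediator definition adds none to regressions (i) to (iii). The multilevel provision deals with clustering, not confounding. The statistical analysis plan might add terms, but the regressions and decision rule are already fixed here. This part does not stand.

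**Conclusion.** The point holds as a weakness in a stated fallback. As written, the rule can declare mediation that is not there in roughly 9% to 59% of trials, or 5% to 40% if Sobel's test is also required. Baseline adjustment brings this to about 1% to 4%. These figures rest on the assumed correlations (0.3 to 0.7 at baseline, 0.5 or 0.7 over time), N = 180, change scores, a total effect of 9/16 SD and no clustering.

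The total-effect requirement is a minor cost at the planned effect and a serious one below it.

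A reader might take this as a threat to the trial's main finding. It is not: the primary analysis of IMAGE-HN at 6 months has its own adjusted model and is untouched. Nor does baseline adjustment make the mediation conclusion safe, since unmeasured confounding remains. The change is worth making because the needed data are already scheduled: Table 1 collects IMAGE-HN, BICSI and the Automatic Thoughts Questionnaire at baseline.

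**What to change.** Revise the fallback in section 9.4.3 as follows:

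1. Include baseline IMAGE-HN, the baseline value of the mediator, site and free flap reconstruction in both the mediator and the outcome models.
2. Base the conclusion on a Monte Carlo (or bootstrap) 95% interval for the indirect effect, in place of the causal-steps rule and Sobel's test. The standard errors should allow for clustering by interventionist and for having only about nine clusters per arm. A bootstrap that resamples interventionists would be fragile with so few.
3. Do not require a significant total effect.
4. Add a sensitivity analysis showing how strong an unmeasured mediator-outcome confounder would have to be to remove the indirect effect.

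The cost is revised wording and a little more analysis work. No new data are needed.

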9.2 SAMPLE SIZE DETERMINATION

The primary endpoint for the proposed RCT is the change in the IMAGE-HN score from baseline to 6-month follow-up. Our primary objective is to test the hypothesis that BRIGHT decreases HNC-related BID from baseline to 6-month follow-up (as measured by clinically significant reduction in the IMAGE-HN score) relative to AC. We target a mean difference in IMAGE-HN score reduction of 9 between BRIGHT and AC at 6 months. This targeted difference is (1) clinically important using widely accepted distribution-based methods of patient reported outcome measure interpretation⁸⁸ and (2) commensurate with clinically meaningful differences in BID among cancer survivors from other appropriately powered trials.^{14,41,100} In our pilot RCT, at 3-months post-intervention (a timepoint similar to 6 month follow-up), BRIGHT improved IMAGE-HN scores from baseline relative to AC (mean model-based difference in change in IMAGE-HN score = -17.1 [90% CI, -25.6 to -8.6] points; $P = 0.002$). The targeted clinically important difference in IMAGE-HN score reduction of 9 thus appears highly feasible. Determining the sample size for the proposed RCT requires adjusting for the clustering of trial participants within psychologist (BRIGHT arm) or HN clinical staff member (AC arm). We expect the number of clusters in each arm to be 9 with an average of 10 trial participants per cluster. We further estimate an intra-class correlation coefficient (ICC) = 0.05^{101,102} and standard deviation = 16 based on similar studies.^{41,100} Given these assumptions, a sample size of $N = 180$ ($n = 90/\text{arm}$) yields 83.7% power to detect the targeted 9-point average reduction in IMAGE-HN scores between the BRIGHT and AC arms with two-sided $\alpha = 0.05$ (PASS v 08.0.13, Inequality Tests for Two Means in a Cluster-Randomized Design module).

Targeting an attrition rate = 20%, we plan to enroll 226 HNC survivors with BID to achieve our target sample size of $N = 180$ evaluable patients for the modified intention-to-treat (ITT) analyses of the efficacy population. In our pilot RCT, 20% (11/54) of eligible patients who accrued to the RCT were not evaluable for the primary endpoint: $n = 7$ (13%) went off study per protocol due to the development of recurrent HNC or a second non-HNC malignancy; and $n = 3$ (7%) withdrew due to intercurrent physical demands. No patients were lost to follow-up.

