9.4.2 ANALYSIS OF THE PRIMARY ENDPOINT

We will use a model-based approach to analyze change in IMAGE-HN score from baseline to 6-month follow-up. Specifically, change in IMAGE-HN score will be modeled using a regression model with a factor for trial arm, covariates for the randomization stratification variable of site and free flap reconstruction, and pre-specified baseline covariates known to be prognostic for the primary endpoint including baseline IMAGE-HN score, gender, education, employment, tumor location, and adjuvant therapy.^{8,75} The selection of pre-specified baseline covariates known to be prognostic follows best practices for randomized clinical trials.¹⁰³ Additionally, adjusting for the baseline score in a change-score analysis is discussed at length by Frank Harrell and James Slaughter.¹⁰⁴ The GEE regression model was selected to account for the clustering of patients within psychologist (BRIGHT arm) or HN clinical staff member (AC arm). Our preferred model-based approach is a marginal model using GEEs because

subsequent inference best aligns with the trial's stated primary objective. Furthermore, GEEs are robust to variance misspecification. We will use GEEs with an identity link and an exchangeable working correlation structure. Final inference will be based on the robust sandwich estimator.

The primary analysis will use the 6-month IMAGE-HN evaluable set, which eliminates unit non-response, that is, patient data where the baseline or 6-month survey is not completed. However, the potential for survey item non-response exists. There are three types of item non-response to consider: (1) the item is missing at baseline and at follow-up; (2) the item is missing at baseline but not missing at follow-up; and (3) the item is not missing at baseline but is missing at follow-up. We expect the rate of item non-response at baseline to be 0% given training of study coordinators and our experience with the pilot study. In the event of item non-response at the 6-month follow-up, we adopt a conservative imputation approach to avoid inflation of treatment effect. Accordingly, we will impute the baseline value for the given item to reflect no change. As a sensitivity analysis, we will also impute the item's value from the most recent follow-up time prior to 6-months. Finally, depending on the extent of missing data, we may additionally perform sensitivity analyses using multiple imputation or treating survey total scores as interval censored.

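### The mediation analysis models interventionist clustering only after a significant pre-test, although the rest of the design treats clustering in both arms as given

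*Protocol*

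**What the plan says.** Section 9.2 builds clustering into the sample size: "Determining the sample size for the proposed RCT requires adjusting for the clustering of trial participants within psychologist (BRIGHT arm") and, for the control arm, within the clinical staff member. It adds: "We expect the number of clusters in each arm to be 9 with an average of 10 trial participants per cluster", with "intra-class correlation coefficient (ICC) = 0.05".

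Section 9.4.2 carries this into the primary model without condition: "The GEE regression model was selected to account for the clustering of patients within psychologist (BRIGHT arm"), and again within staff member for the control arm. The secondary mixed model in the same section includes cluster-specific random effects.

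Section 9.4.3 describes the mediation work as structural equation models for four candidate mediators, with Baron-Kenny regressions as the fallback if the models are unstable. No cluster term appears in either description. Interventionist clustering enters only through this sentence: "If the cluster effect is significant, we will conduct multilevel mediation analysis for partially nested data". The other multilevel model in that section is triggered by temporal variation in the mediating process, not by clustering.

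**The concern.** The same design feature is fixed in the sample size, the primary model and the secondary mixed model, but optional in the mediation analysis. What makes it optional is a significance test that has little power with nine clusters per arm. When that test is not significant, patients are analysed as independent. Treatment is confounded with cluster, since each interventionist is counted in one arm only. The standard error of any treatment contrast is therefore too small if clustering is present and ignored.

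What is at stake is the error rate of the mechanism claims, which are a listed secondary objective. The label 'partially nested' is a smaller matter: it describes a design with one clustered arm, whereas sections 9.2 and 9.4.2 name clusters in both.

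**Working it through.** **Inputs from section 9.2.** 9 clusters per arm, 10 participants each, 90 per arm; ICC 0.05; "standard deviation = 16 based on similar studies"; target difference 9 points; two-sided alpha 0.05.

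**Assumptions not in the protocol.** The IMAGE-HN ICC also applies to the mediators. Clusters are equal in size. The pre-test is a one-way F-test of cluster within arm at level 0.05.

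**1. The protocol's own power.**
- Design effect = 1 + (10 − 1) × 0.05 = 1.45.
- SE = 16 × √(2 × 1.45 / 90) = 2.872.
- Non-centrality = 9 / 2.872 = 3.134.
- A non-central t with 2 × (9 − 1) = 16 df gives 83.67%, against the stated 83.7%.

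The inputs are therefore read as the protocol meant them. The 16 df also show that section 9.2 bases its inference on clusters, not patients.

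**2. Power of the pre-test.** The F statistic has 16 and 162 df, with critical value 1.706. Under clustering it is inflated by 1 + 10 × ICC / (1 − ICC). At ICC 0.05 this factor is 1.526, so power = P(F > 1.706 / 1.526) = P(F > 1.118) = 34%.

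| ICC | Inflation factor | Power at level 0.05 |
|---|---|---|
| 0.02 | 1.204 | 14% |
| 0.05 | 1.526 | 34% |
| 0.10 | 2.111 | 67% |

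Other forms of the test at ICC 0.05 give 31% (boundary-corrected likelihood-ratio test), 23% (one arm only) and 47% (F-test at level 0.10).

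**3. Type I error of the treatment-to-mediator test, nominal 5%.** If clustering is ignored, the error is 2 × [1 − Φ(1.96 / √1.45)] = 2 × [1 − Φ(1.628)] = 10.4%. The two-step rule was simulated from the between- and within-cluster mean squares, using the 16-df cluster-level test after a significant pre-test and the 178-df unclustered test otherwise.

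| ICC | Pre-test level | Two-step rule | Always clustered, 16 df |
|---|---|---|---|
| 0.02 | 0.05 | 6.3% | 5.0% |
| 0.05 | 0.05 | 7.5% | 5.0% |
| 0.10 | 0.05 | 7.2% | 5.0% |
| 0.05 | 0.10 | 6.6% | 5.0% |
| 0.05 | 0.20 | 5.6% | 5.0% |

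At ICC 0.05 and level 0.05, the error among trials whose pre-test is not significant is 10.5%.

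**4. From one path to the mediation claim.** A mediator and an outcome were simulated with no treatment effect on the mediator, a real mediator effect on the outcome, and ICC 0.05. Requiring both paths to be significant, as a stand-in for the SEM indirect effect, gave a false claim in 10.8% of trials with clustering ignored and 7.8% under the two-step rule. The full Baron-Kenny rule in section 9.4.3 also requires the treatment coefficient to shrink. It gave 5.2% even with clustering ignored, because the shrinkage condition discards about half of the false positives.

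**5. Whether always modelling clusters is enough.** At ICC 0.05, a two-level maximum-likelihood model with a normal reference runs at about 7.1%, and an uncorrected sandwich estimator at about 8.3%. The 5.0% needs small-sample inference as well.

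**The case against.** The strongest reply is that the size of the problem rests on inputs the protocol does not give. The ICC of 0.05 is stated only for sizing the IMAGE-HN endpoint, and no value is given for the coping or automatic-thoughts scales. Neither the pre-test nor its level is stated, and a more liberal level shrinks the inflation to 5.6% at 0.20. This stands. It means giving a range, and it rules out saying flatly that the pre-test misses clustering two times in three: at ICC 0.10 it finds it two times in three.

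A reader might also infer that the error rate doubles to about 10%. The protocol does not support that. The 10.4% belongs to a procedure that always ignores clustering, and the 10.5% only to trials with a non-significant pre-test. The rule as a whole runs at about 7.5%.

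Nor does it follow that every mediation claim is made too easily, since the Baron-Kenny rule holds near 5%. That rule is only the fallback, however, and the planned SEM has no shrinkage condition.

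It is also true that small-sample inference accounts for much of the gap between 7.5% and 5.0%. That bears on the wording of the fix, not on whether the condition should go.

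On 'partially nested', the cited method's title covers both fully and partially nested data. The label is a mismatch, and no numerical consequence has been shown. Finally, the point is not a detail left to the SAP: the protocol itself states the rule.

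**Conclusion.** The concern holds in moderate form. Section 9.4.3 makes conditional what sections 9.2 and 9.4.2 treat as part of the design, and the condition is a test with about 34% power at ICC 0.05 (14% at 0.02, 67% at 0.10). The treatment-to-mediator test then runs at about 7.5%, with 6.3% to 7.5% over ICC 0.02 to 0.10 at a 0.05 pre-test level, against 5.0% for an always-clustered small-sample test.

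These figures assume that the IMAGE-HN ICC carries over to the mediators, that there are 18 equal clusters of 10, and that the pre-test is an F-test. The inflation falls on the treatment-to-mediator and treatment-to-outcome paths within the mediation models, and on the SEM indirect effect. The primary analysis is unaffected, because its GEE accounts for clustering without any pre-test. As a secondary analysis with moderate inflation, this rates between minor and should-change.

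**What to change.** Replace the conditional sentence in section 9.4.3 with:

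> All mediation models will account for clustering by interventionist in both arms, regardless of the significance of the cluster effect, using either a two-level model or cluster-robust standard errors, in each case with small-sample inference (cluster-level degrees of freedom or an equivalent correction). If the two-level model does not converge, single-level models with small-sample-corrected cluster-robust standard errors will be used.

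Replace 'partially nested' with wording that matches nesting in both arms. The small-sample requirement must attach to both options, or much of the gain is lost. The convergence fallback is needed because section 9.4.3 itself foresees unstable models.

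The cost is a change of wording before the data are seen, somewhat wider standard errors, and a slightly more complex model for each mediator.
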